15.3.3. Descriptive Analyses

We will use descriptive analyses to summarize subject characteristics of our study populations across treatment groups. Dichotomous variables will be summarized as proportions with 95% confidence intervals. Continuous variables will be summarized using means, standard deviations, and 95% confidence intervals if they are symmetric and unimodal. Otherwise, they will be summarized using the median and the interquartile range. Simple t-, chi-squared, or Fisher's exact test, as appropriate, will be used to compare quantitative measures across treatment groups. The following variables will be summarized:

1. baseline and demographic characteristics
2. use of concomitant medications
3. reasons for early termination
4. all reported AEs

15.4. Interim Analyses

No formal interim analyses of this study are planned.

16.1. Source Data

Source documents and source data are considered to be the original documentation where subject information, visits consultations, examinations and other information are recorded. Documentation of source data is necessary for the reconstruction, evaluation and validation of clinical findings, observations and other activities during a clinical trial.

16.2. Access to Source Data

The site investigators and site staff will make all source data available to the DAIT/NIAID, as well as to relevant health authorities. Authorized representatives as noted above are bound to maintain the strict confidentiality of medical and research information that may be linked to identified individuals.

17. Protocol Deviations

17.1. Protocol Deviation Definitions

Protocol Deviation – The investigators and site staff will conduct the study in accordance to the protocol; no deviations from the protocol are permitted. Any change, divergence, or departure from the study design or procedures constitutes a protocol deviation. As a result of any deviation, corrective actions will be developed by the site and implemented promptly.

Major Protocol Deviation - A Protocol Deviation is a variance from the IRB approved protocol that may affect the subject's rights, safety, or well-being and/or the completeness, accuracy and reliability of the study data. In addition, protocol deviations include willful or knowing breaches of human subject protection regulations, or policies, any action that is inconsistent with the NIH Human Research Protection Program's research, medical, and ethical principles, and a serious or continuing noncompliance with federal, state, local or institutional human subject protection regulations, policies, or procedures.

Non-Major Protocol Deviation - A non-major protocol deviation is any change, divergence, or departure from the study design or procedures of a research protocol that does not have a major impact on the subject's rights, safety or well-being, or the completeness, accuracy and reliability of the study data.

17.2. Reporting and Managing Protocol Deviations

The study site principal investigator has the responsibility to identify, document and report protocol deviations as directed by the study Sponsor. However, protocol deviations may also be identified during site monitoring visits or during other forms of study conduct review.

Upon determination that a protocol deviation has occurred, the study staff will complete a Protocol Deviation form. Protocol deviation reports will be compiled and reviewed by the NIAID/DAIT and the DSMB. Sites will be responsible for reporting deviations to local IRB's, as per local requirements.

18. Ethical Considerations and Compliance with Good Clinical Practice

18.1. Statement of Compliance

This clinical study will be conducted using good clinical practice (GCP), as delineated in *Guidance for Industry: E6 Good Clinical Practice Consolidated Guidance*, and according to the criteria specified in this study protocol. Before study initiation, the protocol and the informed consent documents will be reviewed and approved by each site *IRB*. Any amendments to the protocol or to the consent materials will also be approved by the respective IRB before they are implemented.

18.2. Informed Consent Process

The consent process will provide information about the study to a prospective participant and will allow adequate time for review and discussion prior to his/her decision. The principal investigator or designee listed on the FDA 1572 will review the consent and answer questions. The prospective participant will be told that being in the trial is voluntary and that he or she may withdraw from the study at any time, for any reason. All participants (or their legally acceptable representative) will read, sign, and date a consent form before undergoing any study procedures. Consent materials will be presented in participants' primary language. A copy of the signed consent form will be given to the participant.

The consent process will be ongoing. The consent form will be revised when important new safety information is available, the protocol is amended, and/or new information becomes available that may affect participation in the study.

Appendix 1. Donor Assessments

Visit Number	Screening
	D1
Study Assessments (All Donors)	
Recipient Eligibility and Consent	x
Demographics (Age at Donation, Gender, Ethnicity)	x
Donor HLA Typing (retrospective chart review)	x
EBV and CMV IgG ¹	x
HBV cAb, HBV sAg, HBV sAb quantitative ¹	x
Limited Medical History	x

¹ HLA Typing and viral serologies performed as part of evaluation for donation can be collected retrospectively.

Appendix 2. Group 1 Recipient Schedule of Events

	Study Eligibility	Randomization	Day	Day	Day	Day	Day	Day	Day	Clinically Indicated Biopsy
			41	48	55	69	125	223	405	
Visit Number	Screen 1	Day 0	T0-G1	1	2	3	4	5	6	CIB
Visit Window	± 2 weeks of 6 month biopsy †	≤ 2 weeks after Qualifying Biopsy	± 3 days		± 5 days			± 14 days		- 14 days prior to last study visit
General Study Assessments										
Study Eligibility †	x									
Informed Consent	x									
Randomization		x								
Demographics, Transplant History	x									
Medical History	→	→	→	→	→	→	→	→	→	
Physical Examination/ Vital Signs	x		x	x	x	x	x	x	x	
Review/Collect Concomitant Medications	→	→	→	→	→	→	→	→	→	
Adverse Event/Serious Adverse Event Assessment	→	→	→	→	→	→	→	→	→	
Local Laboratory Assessments										
Recipient HLA Typing ¹	x									
Donor Specific Anti-HLA Antibodies Class 1 and 2 ¹	x							x	x	x
CMV, EBV, HIV1, HIV2, HBV (HBsAg, HBcAb), HCV (HCVAb) serology ¹	x									
CMV, EBV by PCR	x		x	x	x	x	x	x	x	x
BKV by PCR in serum	x							x	x	x
HCV PCR (for subjects with positive HCVAb)	x									
SARS-CoV2 RT-PCR	x ⁴									
CBC (with differential and platelets)	x		x	x	x	x	x	x	x	x
CD4 Count	x			x	x	x	x	x	x	x
PT/INR	x							x ²		x
Basic Chemistry (Na, K, Cl, CO ₂ , BUN, Glucose, Creatinine)	x		x	x	x	x	x	x	x	x
Liver Tests (ALT, AST, T Bilirubin, D Bilirubin)	x		x	x			x	x	x	
Tacrolimus Level	x		x	x	x	x	x	x	x	x ³
Fasting Lipid Panel	x							x	x	x
Urine Protein and Creatinine Ratio	x		x	x	x	x	x	x	x	x
Urine Pregnancy Test	x									
Local Pathology Results - Graft Histology (Standard of Care Biopsy)	x							x		x
Central Laboratory Assessments										
Blood Specimens										
TruCount ³ (UCSFa)	x									
MFC Panels (Percentage Tregs/ Leukocyte phenotypes in Blood) - PBMC (UCSFb)					x	x	x	x	x	x
kSORT and kSPOT (Gene Expression in Blood) - Paxgene Tube (UCSFb)	x				x	x	x	x	x	x
non-HLA Alloantibodies in Blood - 5 ml Red Top Tube (UCSFb)	x				x					
Fibrosis Biomarkers in Serum - Serum from Red Top Tube (UAB)	x				x		x	x	x	x
Renal Biopsy Specimens										
miF/ISH (Intragraft Cytokine Expression) - 1/2 16g Core Formalin Fixed Paraffin-Embedded (UCSFc)	x							x		x
CRM (Transcriptional Profiling of Graft) - performed with FFPE tissue (UCSFc)	x ²							x		x
Pathology Slides (biopsy case) for Central Pathology Reading (UCSFc)	x							x		x
Urine Specimens										
Protein Biomarkers and RNA in Urine (Shared 100ml Urine Collection (Pellet & Supernatant to UCSFb)	x				x	x	x	x	x	x
Fibrosis Biomarkers in Urine (Shared 100ml Urine Collection (Supernatant to UAB)										

† Screening biopsy date must be 5 months after transplant ± 8 weeks. Except as marked, all screening labs should be dated ± 2 weeks of biopsy date, keeping in mind lab results must be available within window for randomization.

¹ HLA Typing, DSA, and viral serologies performed as part of evaluation for transplantation can be collected retrospectively. If not available, serologic testing should be done within 2 weeks of screening biopsy. EBV, should be repeated within screening window if previously negative.

² PT/INR should be collected as part of standard of care assessment prior to biopsy.

³ TruCount will only be performed at the screening visit.

⁴ SARS-CoV2 testing does not have to be repeated if negative at time of biopsy.

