Antibody Mediated Rejection	Diffusely positive staining for C4d, presence of circulating anti-donor antibodies, and morphologic evidence of acute tissue injury.
Graft Inflammation	Banff i1 and/or ti1+ t0, t1, t2 or-t3 or Banff i2 and/or ti2 + t0 or t1
Graft Failure	90 consecutive days of dialysis dependency
Infection, Severe	Study defined grade 3 or higher; culture-proven and clinically diagnosed
Investigational Agent	polyTregs, everolimus
Protocol Mandated Procedures	Any procedure or specimen collection performed solely for the purpose of this research study, not considered site specific standard of care.
Randomized	A subject who met eligibility criteria, signed informed consent document, and was randomly assigned to one of two treatment groups.
Withdrawn from Study Therapy	Subjects who prematurely discontinue the study after receiving polyTregs.
Treatment for Rejection	Treatment of rejection in this protocol constitutes use of IV steroids and/or Thymoglobulin. Adjustment of maintenance immunosuppression medications will not be counted as treatment for rejection.
Women of Childbearing Potential	WOCBP includes any female who has experienced menarche and who has not undergone successful surgical sterilization (hysterectomy, bilateral tubal ligation, or bilateral oophorectomy) or is not postmenopausal (defined as amenorrhea \geq 12 consecutive months; or women on hormone replacement therapy with documented serum follicle stimulating hormone level > 35 mIU/mL). Even women who are using oral, implanted, or injectable contraceptive hormones or mechanical products such as an intrauterine device or barrier methods (diaphragm, condoms, spermicides) to prevent pregnancy or practicing abstinence or where the partner is sterile (e.g., vasectomy), should be considered to be of childbearing potential.

1. Study Hypotheses/Objectives

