4.1.2 Exclusion Criteria

Individuals who meet any of these criteria are not eligible for enrollment as study participants:

1. Inability or unwillingness of a participant to give written informed consent or comply with study protocol
2. History of malignancy; except adequately treated basal cell carcinoma
3. History of graft loss from acute rejection within 1 year after any previous transplant
4. History of transplant renal artery stenosis
5. History of cellular rejection prior to enrollment that did not respond to steroids and/or subsequent creatinine after treatment for rejection greater than 15% above baseline
6. Known hypersensitivity to mTOR inhibitors or contraindication to everolimus (including history of wound healing complications)
7. Any chronic illness requiring uninterrupted anti-coagulation after kidney transplantation
8. Post-transplant DSA >5000 MFI or post-transplant treatment with IVIg for DSA. Enrolled subjects with post-transplant DSA >2000 MFI will not be eligible for mTOR conversion.
9. Positive HIV 1 or HIV 2 serology prior to transplantation
10. Known positive HBSAg, or HBcAB serology
11. Proteinuria with urine pr/cr > 1.0 g/g
12. Any condition requiring chronic use of corticosteroids >10mg/day at the time of study entry
13. Subjects requiring treatment for pathologic findings on study eligibility biopsy (see inclusion 4).
14. Active infection at the time of study entry
15. History of active TB or latent TB without adequate treatment (see inclusion 10)
16. Serum BK virus >1,000 copies/ml by PCR at the time of study entry
17. Hematocrit <27%; ANC < 1,000/ μ L; lymphocytes <500/ μ L at the time of study entry
18. Participation in any other studies with investigational drugs or regimens in the preceding year
19. Any condition or prior treatment which, in the opinion of the investigator, precludes study participation
20. Unable to provide adequate biopsy specimen (paraffin embedded formalin fixed) from eligibility biopsy (3-7 months post-transplant) for quantitative analysis.
21. EBV naïve recipient of a kidney from an EBV positive donor, historically EBV naïve recipient with primary EBV infection at the time of screening (primary anti-VCA IgM, without antibody to EBNA), positive EBV PCR
22. Hepatitis C Virus Ab positive subjects with negative HCV PCR are eligible if they have spontaneously cleared infection or are in sustained virologic remission for at least 12 weeks after treatment.
23. Positive SARS-CoV2 testing by RT- PCR

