4.2. Treg Infusion Eligibility Criteria

4.2.1. Treg Infusion Inclusion Criteria

1. Individuals randomized to group 2 who continue to meet all of the enrollment criteria.
2. Negative SARS-COV2 RTPCR within 1 week of Treg infusion

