4.2.2. Treg Infusion Exclusion Criteria

Individuals randomized to group 2 who meet any of these criteria are not eligible for Treg infusion:

1. Received any vaccination within 14 days prior to blood collection for Treg manufacture
2. Unacceptable Treg product
3. Positive pregnancy test for women of childbearing potential

4.3. mTOR Conversion Eligibility Criteria

4.3.1. mTOR Conversion Inclusion Criteria

Individuals who meet all of these criteria are eligible for mTOR conversion:

1. Received at least 300×10^6 polyTreg infusion
2. Resolution of inflammation on the 2-week post-infusion biopsy as compared to the baseline biopsy, confirmed by central pathologist

4.3.2 mTOR Conversion Exclusion Criterion

Individuals who meet any of these criteria are not eligible for mTOR conversion:

1. Post-transplant DSA >2000 MFI
2. Any condition or clinical variable, which in the opinion of the site investigator, precludes conversion to mTOR.

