6.1.3. Everolimus Study Dosing and Administration

The use of everolimus in this trial will deviate from package instructions. Subjects in this trial are enrolled between 3 and 7 months after transplantation and induction therapy is site-specific (not study mandated). Furthermore, subjects will be on tacrolimus at study entry, rather than cyclosporine. In eligible patients, everolimus will be initiated within 2 weeks after kidney biopsy showing resolution of inflammation following Treg infusion. Everolimus will be initiated at a dose of 1.5 mg orally twice daily and titrated, as needed. Subjects will begin everolimus with target trough levels of 3-8

$\mu\text{g/L}$ for 4 weeks while still taking tacrolimus. Everolimus target trough levels will be 6-10 $\mu\text{g/L}$ when tacrolimus is discontinued.

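### The screening footnote accepts a DSA result from the transplant work-up, which cannot test the post-transplant DSA limits set for enrolment and everolimus conversion

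*Protocol*

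**What the plan says.** Three eligibility rules depend on DSA.

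- **Enrolment.** Protocol Section 4.1.2, item 8, excludes "Post-transplant DSA >5000 MFI or post-transplant treatment with IVIg for DSA". The same item adds: "Enrolled subjects with post-transplant DSA >2000 MFI will not be eligible for mTOR conversion".
- **Infusion.** Section 4.2.1 admits "Individuals randomized to group 2 who continue to meet all of the enrollment criteria", which brings item 8 forward to the infusion visit.
- **Conversion.** Section 4.3.2 lists "Post-transplant DSA >2000 MFI" as its first exclusion.

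The SAP repeats the enrolment, infusion and conversion criteria in its Section 3 summary.

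The schedules say where the DSA value comes from. In Appendix 2 (Group 1) the DSA row carries footnote 1: "HLA Typing, DSA, and viral serologies performed as part of evaluation for transplantation can be collected retrospectively". It continues: "If not available, serologic testing should be done within 2 weeks of screening biopsy". Appendix 2 also requires screening labs to fall within 2 weeks either side of the biopsy, but exempts rows that are marked otherwise. Appendix 3 (Group 2) contains the same retrospective-collection sentence as note 2.

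**The concern.** Each limit is set on DSA measured after the transplant. A result from the evaluation for transplantation was obtained before it. Such a result cannot show antibody that has formed against the graft since then, yet the footnote lets it fill the screening DSA cell. A site could follow the schedule exactly and still hold no value that answers item 8.

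Two later decisions inherit the gap: giving the infusion, and replacing tacrolimus with everolimus. If no post-transplant value is obtained at screening, and none is scheduled before those decisions, a participant above a stated limit could be enrolled, infused or converted without the schedule exposing it.

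**Working it through.** The documents give no figure to reproduce here. The check sets the passages side by side and adds visit-day arithmetic.

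**1. Value required and value secured at enrolment**

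| | Required | Secured by the schedule |
|---|---|---|
| Item 8 | Post-transplant DSA | Work-up DSA accepted (Appendix 2, footnote 1) |
| New test | Needed if only a work-up result exists | Asked for only if no result is available |
| Date rule | – | ±2 weeks of biopsy, but marked rows are exempt and the DSA row is marked |

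The same footnote requires EBV to be repeated in the screening window if previously negative, and has no such clause for DSA. The donor footnote in Appendix 1 lists only HLA typing and viral serologies. Both comparisons suggest that DSA was swept in with tests that do not need a current value.

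**2. Age of an accepted work-up result.** The eligibility biopsy is at 5 months ± 8 weeks. Taking 5 months as 5 × 30.44 = 152 days and 8 weeks as 56 days, the biopsy falls 152 − 56 = 96 to 152 + 56 = 208 days after transplant. A result that predates the transplant is older than that.

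**3. Footnote numbering in Appendix 3.** The DSA row shows marker 1. Note 1 there is the rule that screening labs be drawn within ±2 weeks of the biopsy; the retrospective sentence is note 2. Read literally, the Group 2 row falls under the date rule and the Group 1 row does not, although participants are screened before they are assigned to a group. The trough-level note also looks off by one, so the markers have probably shifted.

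**4. Between screening and infusion.** Counting cells in the Appendix 3 DSA row, the marks are in columns 1, 10, 11 and 12. Items tied to the infusion visit (Treg eligibility, pregnancy test, serum banking) are in column 6, and collection comes earlier. Under any alignment, no DSA mark falls between Screen 1 and infusion. Other eligibility tests are repeated: the blood count before collection, SARS-CoV2 within 1 week of infusion, and the pregnancy test before infusion.

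**5. Before conversion.** Section 6.1.3 says "everolimus will be initiated within 2 weeks after kidney biopsy showing resolution of inflammation following Treg infusion". The biopsy is at Day 14 ± 3, so the latest start is 14 + 3 + 14 = Day 31 after infusion. The first DSA mark after screening is in column 10, which can be read three ways:

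- Day 84 by the printed header, 84 − 31 = 53 days after the latest start.
- Day 182 by analogy with Group 1, where DSA falls at Day 223 and 223 − 41 = 182; that is 182 − 31 = 151 days after the latest start.
- Day 28, because the Day 14 biopsy items sit in column 9 and the mTOR-eligibility mark shares column 10 with DSA. Conversion may begin before Day 28, so even this reading does not assure a prior result.

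**6. If DSA is drawn in the screening window.** Let L be the unstated lag from biopsy to central confirmation. A sample taken 14 days before the biopsy could be 14 + L + 62 = 76 + L days old at infusion, and 76 + L + 17 + 14 = 107 + L days old at conversion.

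**The case against.** The strongest reply is that the criteria already govern. They say post-transplant, the footnote is permissive and waives no criterion, and Screen 1 has a DSA cell in both schedules. An investigator certifying item 8 must hold a post-transplant value, and sites may test as routine care. This stands in part: a participant enrolled above the limit would breach the criteria. But the schedule tells the site which result may fill that cell, and it names one that cannot answer the criterion. The passages conflict.

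Item 8 also states the 2000 MFI conversion bar, so one post-transplant screening value might be meant to serve both limits. That is a fair reading, and the plan sets no maximum age for the result, so the 107 + L days above breach no stated rule. The plan does not, however, say that the screening value is the one to use.

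Three stronger inferences are not supported:

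- *That no DSA precedes conversion.* The Appendix 3 columns are broken in the available text, and a mark at the mTOR-eligibility visit cannot be excluded.
- *That antibody-mediated rejection cannot be established at the Day 14 biopsy,* because its definition includes "Diffusely positive staining for C4d, presence of circulating anti-donor antibodies, and morphologic evidence of acute tissue injury". The biopsy is read centrally, and nothing bars an unscheduled DSA test.
- *That antibody present before treatment cannot be told from antibody arising later.* Section 11.4 banks Group 2 serum and plasma on infusion day before dosing and names DSA among possible tests. Such testing is optional, so it secures no eligibility check, but a baseline sample exists for that group.

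Nor do the documents say how many recipients have a work-up DSA on file, so the number of sites or participants that would rely on the footnote is unknown.

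**Conclusion.** The point holds as a contradiction within the protocol. Appendix 2 footnote 1 admits a pre-transplant DSA at screening, while item 8 and Section 4.3.2 set limits on post-transplant DSA. Appendix 3 adds a conflict of footnote markers. No DSA is scheduled between Screen 1 and infusion despite Section 4.2.1, and this does not depend on how the table is aligned. A DSA result before conversion is not assured.

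The enrolment rule applies to all 14 planned participants, and the infusion and conversion rules to the 7 planned for polyTregs. These are the numbers subject to the rules. They do not estimate how many would exceed a limit, for which the documents give no basis. The conclusion assumes only that a result obtained during evaluation for transplantation predates the transplant. Confidence is high for the footnote and the infusion step, and lower for conversion because of the broken table.

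**What to change.** 1. Remove DSA from the retrospective-collection footnote in Appendices 2 and 3, leaving HLA typing and viral serologies there. The screening DSA then falls under the same ±2-week rule as the other screening labs, and is the post-transplant value that item 8 already calls for.
2. Correct the footnote markers in Appendix 3 so that each row points to the intended note.
3. Reconcile both schedules with item 8, Section 4.2.1 and Section 4.3.2, and state which post-transplant DSA result serves the infusion check and which serves the conversion check. Whether that is the screening value or a later one is for the sponsor and investigators to decide. The MFI limits are not in question.

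For anyone already enrolled, a listing of the date of the DSA result used for each eligibility decision would show whether the gap had any effect.

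The cost is an amendment to a footnote and its markers, a clarifying sentence, and a screening DSA for participants without a current one. Some candidates who would have passed on an old result may fail screening.
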